Comparison of Outcomes in Patients Undergoing Endoscopic
Retrograde Cholangiopancreatography (ERCP) Using
Duodenoscope with Single-use Distal Cover and Conventional
Reusable Duodenoscope: A Randomized Controlled Trial

Study Protocol and Statistical Analysis Plan

NCT05429203

September 22, 2022

Background and Rationale

Over the past decade, multiple outbreaks of infections due to drug-resistant organisms have been traced to contaminated conventional reusable duodenoscopes. While lapses in reprocessing protocols may contribute, the inherent design of reusable duodenoscopes has also been implicated.

Despite enhanced reprocessing guidelines issued by the FDA, persistent contamination remains a concern. Studies report that **3–5%** of duodenoscopes continue to yield positive cultures even after reprocessing. In response, duodenoscope manufacturers have introduced models with **disposable distal end caps (DDEC)** intended to improve reprocessing efficacy and reduce infection risk.

However, these DDEC duodenoscopes have been linked with specific adverse events such as detachment of the distal cap, rigidity, scope fracture, contamination, imaging issues, and functional failure. To date, **no large-scale or long-term comparative study** has evaluated procedure success and complication rates between DDEC and **conventional reusable duodenoscopes (CRD)**.

Study Objective

To compare:

- Procedure-related complication rates (primary outcome)
- Procedure success rates and technical performance characteristics (secondary outcomes)

in patients undergoing ERCP with either DDEC or CRD.

Study Design

- **Design Type:** Prospective, randomized controlled trial
- **Sample Size:** 600 patients (300 per group)
- **Setting:** Stanford Hospital Endoscopy Unit
- **Randomization:** Block randomization with equal allocation
- **Follow-Up:** Phone calls at 1 week, 1 month, and 3 months to assess delayed complications

Study Population

Inclusion Criteria:

1. Age > 18 years
2. Undergoing ERCP for biliary or pancreatic indications

Exclusion Criteria:

1. Vulnerable groups (e.g., pregnant women)

2. Inability to provide informed consent
3. Known cholangitis
4. Known infection with CRE or other MDRO
5. Surgically altered anatomy (except Billroth I)

Study Interventions

Participants will be randomized to undergo ERCP using one of the following duodenoscopes:

- **Group A:** Duodenoscope with Disposable Distal End Cap (DDEC)
- **Group B:** Conventional Reusable Duodenoscope (CRD)

Both scopes are **FDA-approved** and considered standard of care.

Outcome Measures

The primary outcome measured in this study is the total patient complication rate, which includes cap detachment, severe mucosal injuries, post-ERCP pancreatitis, post-sphincterotomy bleeding, perforation, cholangitis, abdominal pain, fever, and procedure-related death. Secondary outcomes include the overall procedure success rate; successful intubation rates at key anatomical checkpoints (oropharyngeal/esophageal, gastroesophageal junction, and pyloric/duodenal regions); occurrence of suboptimal papillary positioning; total procedure time; cannulation time; fluoroscopy time and total radiation dose; use of advanced cannulation techniques; inadvertent duct cannulation; and need for crossover to an alternate duodenoscope due to technical failure or procedural difficulty.

The initial sample size was determined based on an expected complication rate of 7% in the CRD group and 14% in the DDEC group. Assuming a 1:1 randomization, alpha error of 0.05, and study power of 80%, a total of 600 patients (300 per group) were required. Interim analyses were conducted during the study to assess efficacy and futility using conditional power analysis calculated with the frequentist Z-statistic method.

- **Maneuverability:** Scored on a validated 5-point scale (1 = Easy; 5 = Unable to complete the required maneuver)
- **Mechanical Characteristics:** Scope stiffness, air-water button functionality, elevator efficiency, and hand strain (each scored on a 5-point scale)
- **Imaging Characteristics:** Image quality and image stability (each scored on a 5-point scale)

Data Collection and Analysis

- **Data Collection:**
Conducted prospectively by evaluators during and after the procedure
- **Statistical Analysis:**
 - Categorical variables compared using chi-square or Fisher's exact tests, as appropriate
 - Analysis conducted using the **intention-to-treat** approach
 - **Software:**
 - *IBM SPSS Statistics v29.0.2.0* (IBM Corp, Armonk, NY)
 - *R v4.2.2* for conditional power analysis (R Foundation for Statistical Computing, Vienna, Austria)

Ethical Considerations

- IRB approval will be obtained prior to initiation
- Written informed consent will be obtained from all participants
- Data will be stored securely in compliance with HIPAA regulations
- Adverse events will be monitored and reported in accordance with institutional guidelines

Figure 1: Study flow diagram

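### No endoscopist stratum or adjustment is described; adding endoscopist as a factor would cheaply sharpen the secondary score and time comparisons

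*Combined protocol and SAP*

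**What the plan says.** Under Study Design, the randomisation entry reads in full "Block randomization with equal allocation". It gives no stratification factor and no block size. The setting is the "Stanford Hospital Endoscopy Unit"; how many endoscopists work there, and how experienced they are, is not stated.

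The outcome section lists "total procedure time; cannulation time; fluoroscopy time and total radiation dose" among the secondary outcomes. It adds a maneuverability score ("1 = Easy; 5 = Unable to complete the required maneuver") and 5-point ratings of stiffness, elevator performance, hand strain and image properties.

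Under Data Collection and Analysis, data collection is "Conducted prospectively by evaluators during and after the procedure". Whether these evaluators are the endoscopists is not said. The only comparison stated is "Categorical variables compared using chi-square or Fisher's exact tests, as appropriate", with analysis by intention to treat. No covariate, stratified test or model is named. The times and radiation dose have no stated method, and the 5-point scores have none unless they are treated as categorical. The documents mention neither endoscopist nor operator.

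**The concern.** Technical performance is a stated objective, and several of its measures describe a person using a device: hand strain, whether a manoeuvre could be completed, time to cannulate. It is reasonable to expect operators to differ on these whichever scope they use. The informative contrast is then DDEC against CRD in the same hands.

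If several endoscopists contribute and the analysis ignores them, the spread between operators stays in the error term. An operator's cases can also fall unevenly between arms by chance. What is at stake is precision on the secondary scores and times: wider intervals and lower power than the same 600 patients could give.

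**Working it through.** **Inputs from the documents.** 300 per arm; alpha 0.05 (taken as two-sided, since the sidedness is not stated); power 80%; "expected complication rate of 7% in the CRD group and 14% in the DDEC group".

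**Inputs assumed.** The ICC, meaning the share of an outcome's variance that lies between operators, at 0.05 to 0.30; a difference of 0.2 SD on a score or time; the number of operators and their complication rates. The documents give none of these.

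**1. The plan's own figure.** With pooled variance and no continuity correction, the mean rate is 0.105 and

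n = [1.960 × √(2 × 0.105 × 0.895) + 0.842 × √(0.07 × 0.93 + 0.14 × 0.86)]² / 0.07² = 300 per arm.

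The stated 600 is reproduced exactly, and power at 300 per arm is 80.0%. Nothing below changes this number.

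**2. Loss of precision on scores and times.** With total SD 1, the standard error of the arm difference is √(2/300) = 0.0816 unadjusted. Removing the between-operator variance multiplies it by √(1 − ICC). Power is approximately Φ(0.2/SE − 1.960), and the difference detectable with 80% power is (1.960 + 0.842) × SE. This uses a normal approximation, treats the 5-point scores as roughly continuous, and ignores the few degrees of freedom spent on operators.

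| ICC (assumed) | Variance ratio 1/(1 − ICC) | Unadjusted 300 per arm is worth | Detectable difference, adjusted (SD) | Power for 0.2 SD, adjusted |
|---|---|---|---|---|
| 0.05 | 1.05 | 285 | 0.223 | 71% |
| 0.10 | 1.11 | 270 | 0.217 | 73% |
| 0.20 | 1.25 | 240 | 0.205 | 78% |
| 0.30 | 1.43 | 210 | 0.191 | 83% |

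Unadjusted, the detectable difference is 0.229 SD and the power for 0.2 SD is 69%. The gain therefore runs from 2 to 14 power points.

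**3. Chance imbalance.** Without stratification, the between-arm difference in the share of cases done by an operator with caseload share q has SD √(2q(1 − q)/300). For q = 1/4 this is 3.5 percentage points (95% range about ±6.9); for q = 1/3 it is 3.8 points (about ±7.5).

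**4. Validity.** Trials of 600 patients with no device effect were simulated with 3 or 6 operators and ICC 0.1 or 0.3 (10,000 trials per setting). The unadjusted test rejected in 4.7% to 5.1% of them. Because patients are individually randomised, ignoring operator does not inflate the type I error.

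**5. Primary outcome.** With three equally busy operators and assumed rates of 3/7/11% on CRD and 6/14/22% on DDEC (averaging the planned 7% and 14%), simulated power over 5,000 trials was 81.2% unadjusted and 81.6% with a test stratified by operator. The simulation error of each figure is about √(0.81 × 0.19/5000) = 0.55 points, so the gap is negligible.

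**The case against.** The strongest reply is that the plan is silent rather than wrong. It does not say that a single unit-wide list was used, or that operator was left out; stratification may exist and simply not be described. With one endoscopist the point disappears. Operator dependence is inferred from the nature of the items; the maneuverability scale is called validated, and the evaluators may not be the operators. For the times and dose, the missing method is a separate gap: the unadjusted comparison used as reference above is the natural extension of the plan, not something it states. At ICC 0.05 to 0.10 the gain is only 2 to 4 power points. All of this stands, and it limits the point to a precision improvement under stated assumptions.

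A reader might infer more in three directions, none of which the documents support:

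- *That operator imbalance biases the device comparison, or that repeated ratings by one person invalidate the tests.* Chance imbalance is ordinary sampling error that the test already allows for, and type I error stays near 5%.
- *That the primary result is threatened.* If an operator's complication rate were 10 points above colleagues' (assumed), a 3.5-point imbalance would move the arm difference by 0.10 × 3.5 = 0.35 points, against a planned difference of 7 points.
- *That adjustment would show whether a DDEC excess belongs to one operator.* A main effect or a pooled Mantel-Haenszel estimate cannot show that; it needs an operator-by-device interaction.

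**Conclusion.** The point holds as a low-severity improvement confined to the secondary scores, times and radiation dose. It assumes that more than one endoscopist takes part and that operators differ on these outcomes. On those assumptions, ignoring operator costs between 2 power points (ICC 0.05) and 14 (ICC 0.30) for a 0.2 SD difference; equivalently, 300 patients per arm do the work of 285 down to 210. Neither the ICC nor the 0.2 SD comes from the documents, so the range matters more than any single value. The sample size and the type I error are unaffected, and the power of the primary comparison is practically unchanged. The documents do not support calling the randomisation defective or the planned primary test invalid.

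**What to change.** - State how many endoscopists take part, who assigns the scores, and whether randomisation was stratified.
- Record the performing endoscopist for each case, and the rater if different. The documents list no data fields, so the sponsor should confirm that this is captured. Where a second operator takes over, define the factor as the endoscopist assigned to start the case, so that the device cannot influence it.
- In the SAP, include endoscopist as a factor, with low-volume operators pooled, in the between-arm models: for example an ordinal or linear model for the scores, and a linear model on the log scale for times and radiation dose.
- Keep the stated unadjusted test for the primary outcome. Add an endoscopist-stratified Mantel-Haenszel analysis as a sensitivity analysis only.
- If the question is whether a device difference is confined to one operator, specify an exploratory operator-by-device interaction.
- Do not change the randomisation list once enrolment has begun. The plan speaks of interim analyses in the past tense, so that stage appears to have passed. Per-operator blocks could also make the next allocation easier to guess, since operators know which scope they hold.

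The cost is a short SAP addition, slightly more analysis work and a few degrees of freedom out of 600 patients. No extra patients or procedures are needed. The additions should be dated and fixed before the arms are compared on these outcomes, so that the choice between adjusted and unadjusted results is not made after seeing them.

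### Three cannulation outcomes have no analysis by papilla status; the all-patient comparison is unbiased but may be less sensitive than a cheap stratified analysis

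*Combined protocol and SAP*

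**What the plan says.** Under Study Population, the second inclusion criterion admits patients "Undergoing ERCP for biliary or pancreatic indications". There are five exclusions, and the only anatomical one is surgically altered anatomy, with Billroth I allowed. Neither prior sphincterotomy nor repeat ERCP is mentioned there. In the whole document, sphincterotomy appears only in the name of one component of the primary composite, bleeding after sphincterotomy.

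Under Study Design, randomisation is described as "Block randomization with equal allocation", with no stratification factor.

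Under Outcome Measures, the secondary outcomes include "cannulation time; fluoroscopy time and total radiation dose; use of advanced cannulation techniques; inadvertent duct cannulation". No analysis set, denominator or expected value is given for any of them.

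Under Data Collection and Analysis, the approach is "intention-to-treat" and the only comparison stated is "Categorical variables compared using chi-square or Fisher's exact tests, as appropriate". No covariate or subgroup is named, and no method is given for a continuous outcome such as cannulation time. The sample size rests on the complication rate alone.

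**The concern.** Cannulation time, advanced techniques and inadvertent duct cannulation measure how hard it is to enter the intended duct. It is plausible that this is easier once the papilla has been cut, so that a difference between scopes has less room to show in those patients. The documents do not say so, and it is used here as an assumption.

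If it is true, two things follow for an unadjusted all-patient analysis. The absolute difference becomes an average of the native-papilla difference and something near zero. For cannulation time, the gap between the two kinds of patient also adds variance that has nothing to do with the scope.

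Technical performance is a stated objective, and the Background lists rigidity and functional failure among the concerns with the disposable-cap scope. A small or non-significant cannulation result would be hard to interpret without knowing how many patients had a native papilla and what happened in them.

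**Working it through.** **The plan's own figure.** For 7% v 14%, two-sided alpha 0.05, power 80%, pooled variance and no continuity correction:

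n = [1.96·√(2·0.105·0.895) + 0.8416·√(0.07·0.93 + 0.14·0.86)]² / 0.07² = (0.8497 + 0.3625)² / 0.0049 = 299.9

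This gives 300 per arm and 600 in total, as stated. Nothing below changes it.

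**Inputs for the cannulation outcomes.** From the plan: 300 per arm, and alpha 0.05 taken as two-sided. Assumed, because the documents give no values:
- f, the native-papilla share: 40% to 90%.
- Cannulation time: native-papilla means 8 v 10 min, SD 6; other patients 2 min in both arms, SD 2.
- Advanced techniques: native papilla 15% v 25%; other patients 2% in both arms.

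**Cannulation time.** The all-patient difference is 2f min. Three standard errors are compared:
- Unadjusted, all patients: √[(V₁ + V₂)/300], with V₁ = W + f(1−f)(8−2)², V₂ = W + f(1−f)(10−2)² and W = 36f + 4(1−f).
- Adjusted for papilla status, all patients: √(2W/300).
- Native papilla only, where the difference is 2 min: √[2·36/(300f)].

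Power is Φ(difference/SE − 1.96). At f = 0.5:
- W = 20, V₁ = 29, V₂ = 36.
- Unadjusted: SE = √(65/300) = 0.466; 1.0/0.466 = 2.15; power 57.5%.
- Adjusted: SE = √(40/300) = 0.365; 1.0/0.365 = 2.74; power 78%.
- Native only: SE = √(72/150) = 0.693; 2.0/0.693 = 2.89; power 82%.

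| Native share | All-patient difference (min) | All patients, unadjusted | All patients, adjusted | Native only |
|---|---|---|---|---|
| 40% | 0.8 | 45% | 67% | 73% |
| 50% | 1.0 | 57.5% | 78% | 82% |
| 60% | 1.2 | 70% | 86% | 88.5% |
| 70% | 1.4 | 81% | 92% | 93% |
| 90% | 1.8 | 95% | 97% | 97% |

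**Advanced techniques.** Power is Φ{[d − 1.96·√(2p̄(1−p̄)/n)] / √[(p₁(1−p₁) + p₂(1−p₂))/n]}. At f = 0.5:
- All patients: 0.5·15 + 0.5·2 = 8.5% v 0.5·25 + 0.5·2 = 13.5%, a 5-point difference; (0.05 − 0.0501)/0.0255 ≈ 0; power 49.9%.
- Native only, 150 per arm: 10 points; (0.10 − 0.0905)/0.0458 = 0.21; power 58.2%.

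At other shares, all patients v native only: 68.1% v 72.8% at 70% native, and 81.7% v 83.0% at 90%.

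**Sensitivity to the zero-effect assumption, at 50% native.**
- Let the other patients differ by 2% v 4%. The all-patient rates become 8.5% v 14.5% and power is 63.5%, above the 58.2% for native only. The ordering reverses.
- Let the other patients' mean times be 2.0 v 2.5 min. The all-patient difference is 0.5·2 + 0.5·0.5 = 1.25 min. V₂ becomes 20 + 0.25·7.5² = 34.06, so the unadjusted SE is √(63.06/300) = 0.458 and power is 78%. The adjusted SE stays at 0.365; 1.25/0.365 = 3.42; power 93%. Native only remains 82%.

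For cannulation time, the adjusted all-patient analysis beats the unadjusted one in every scenario shown. Restricting to native papilla does not always beat the adjusted all-patient analysis.

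**The case against.** The strongest reply is that nothing here is an error. The objective is to compare the scopes in patients undergoing ERCP, the analysis is by intention to treat, and under randomisation the all-patient contrast answers that question without bias. A native-papilla contrast answers a narrower question. That stands, and it is why the native-papilla set should not replace the all-patient analysis.

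It is also fair that the size is assumed throughout. The halving at 50% native comes from setting the effect in the other patients to exactly zero, and it applies to the absolute difference. The risk ratio hardly moves: 25/15 = 1.67 in native papilla v 13.5/8.5 = 1.59 overall. For the binary outcome both analyses are underpowered and the ordering can reverse. All of this stands.

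Three stronger readings are tempting, and the documents do not support them:
- That the whole technical comparison is diluted. The argument reaches three secondary outcomes. It is not shown to reach the intubation checkpoints, maneuverability, or the mechanical and imaging scores.
- That the trial could wrongly declare the scopes equivalent for cannulation. The plan has no equivalence or non-inferiority hypothesis and no margin.
- That the plan explicitly analyses these outcomes in every randomised patient. This is inferred from the intention-to-treat statement; no denominators are given.

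What survives is that the entry criteria allow both kinds of patient, the plan is silent on papilla status, and adjusting for it keeps the all-patient question while recovering precision for cannulation time.

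**Conclusion.** The point holds as a cheap improvement to three secondary outcomes. It is not a flaw in the trial's main comparison. The plan neither stratifies nor adjusts for papilla status and gives no native-papilla result for cannulation time, advanced techniques or inadvertent duct cannulation.

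If patients with a prior sphincterotomy show little scope effect, the absolute all-patient difference is about f times the native-papilla difference. For cannulation time under the assumed inputs, adjustment raises power by about 20 points at 50% native (57.5% to 78%) and by about 2 points at 90% native (95% to 97%). For the binary outcomes the gain is small and not assured.

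These sizes rest on an assumed native-papilla share, assumed times, SDs and rates, and an assumed near-absence of effect after prior sphincterotomy. A reader might infer bias, or a fault in the primary composite or the sample size. Neither follows: the comparison is randomised, and 600 reproduces from the plan's own inputs.

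**What to change.** - Record papilla status (native or prior sphincterotomy) from the patient's history before randomisation. Status as seen at endoscopy will not do, because the assigned scope is then already in use.
- Keep the all-patient intention-to-treat comparison for the three cannulation outcomes, but stratify or adjust it for papilla status. Name the method for cannulation time, which the plan currently lacks.
- Prespecify the native-papilla result for the same three outcomes and report it alongside, with the number of patients in each stratum. Status fixed before randomisation preserves the randomised comparison within the subset.
- Using papilla status as a randomisation stratum is optional. It helps balance but does not cure dilution; the analysis does that. If enrolment is already complete, adjustment and the subset result are still possible from history that predates randomisation.
- Leave the primary composite in all patients. If bleeding is also reported among patients who had a sphincterotomy, label it descriptive, because that denominator arises after randomisation and the scope could influence it.

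The cost is one baseline item, a few sentences in the SAP and one extra analysis. The native-papilla result will rest on fewer patients and be less precise for that reason.

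### Does the plan need a definition of procedure success and a rule for procedures finished with the other duodenoscope?

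*Combined protocol and SAP*

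**What the plan says.** The Background and Rationale says that no large-scale or long-term comparison "has evaluated procedure success and complication rates between DDEC and" conventional reusable scopes. The Study Objective then makes procedure success a secondary comparison. In Outcome Measures the outcome is only named: "Secondary outcomes include the overall procedure success rate". The same list ends with "need for crossover to an alternate duodenoscope due to technical failure or procedural difficulty", so a change of scope is foreseen and counted. Also listed are "total procedure time; cannulation time; fluoroscopy time and total radiation dose", and the maneuverability scale ends at "5 = Unable to complete the required maneuver".

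Under Data Collection and Analysis, the one line that bears on crossover is "Analysis conducted using the intention-to-treat approach". Data collection is described as "Conducted prospectively by evaluators during and after the procedure".

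No section gives criteria for success, a rule for a procedure completed after a change of scope, or a statement of which scope the 5-point scores describe.

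**The concern.** The plan foresees the event that makes success ambiguous and gives no rule for it. Take a patient randomised to the disposable-cap scope whose procedure is finished with the other scope. Intention-to-treat keeps that patient in the disposable-cap arm, but the procedure could be entered there as a success or as a failure. Two analysts could therefore report different success rates from the same patients.

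The scores raise a similar question: a crossed-over patient could get a 5 for the first scope or a low score for the second. Times and radiation dose might be thought to stop at the switch or to run to the end.

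At stake is a device comparison that the Background presents as new. If most failures with the assigned scope are rescued and rescues count as successes, the success rates converge. The plan also says "Interim analyses were conducted during the study to assess efficacy and futility", which could suggest that a definition settled late might be influenced by results already seen.

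**Working it through.** **1. The plan's own figure.** Inputs from Outcome Measures: complication rates 7% and 14%, alpha 0.05 (taken as two-sided), power 80%, equal allocation. With pooled variance and mean rate 0.105:

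n = [1.96·√(2·0.105·0.895) + 0.8416·√(0.07·0.93 + 0.14·0.86)]² / 0.07² = 299.9, so 300 per arm and 600 in total.

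This reproduces the plan. The calculation uses complication rates only, so the definition of success does not enter it.

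**2. How the two readings differ.** The documents give no failure, crossover or rescue rates, so everything in this step is assumed. Let f be the share of procedures that fail with the assigned scope, c the share of failures crossed over and r the share of those rescued, with c and r equal in both arms.

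- Assigned-scope reading: failure = f.
- Any-scope reading: failure = f·(1 − c·r), so the difference between arms shrinks by the factor 1 − c·r.

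Power is by exact binomial enumeration with 300 per arm at two-sided 0.05. The test is the uncorrected chi-square if the smallest expected count is at least 5, and otherwise Fisher's exact test.

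| Assumed f, CRD vs DDEC | c·r | Difference (points) | Power |
|---|---|---|---|
| 3% vs 8% | 0 (assigned scope) | 5.0 | 79% |
| 3% vs 8% | 0.125 | 4.4 | 73% |
| 3% vs 8% | 0.40 | 3.0 | 55% |
| 3% vs 8% | 0.60 | 2.0 | 38% |
| 3% vs 8% | 0.90 | 0.5 | 2% |
| 3% vs 5% | 0 (assigned scope) | 2.0 | 24% |
| 3% vs 5% | 0.40 | 1.2 | 16% |
| 2% vs 4% | 0 (assigned scope) | 2.0 | 30% |
| 2% vs 4% | 0.40 | 1.2 | 17% |

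The choice matters for power when the true difference is large and most failures are rescued. With a 2-point difference, the success comparison has little power on either reading.

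**3. What the separate crossover outcome recovers.** Under 3% vs 8%, the crossover rate is c·f. Its comparison has power 18%, 48%, 65% and 79% at c = 0.25, 0.5, 0.75 and 1. It matches assigned-scope success only when every failure is crossed over.

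**4. One invented data set.** DDEC: 24 failures, 12 crossed over, 10 rescued. CRD: 9 failures, 4 crossed over, 3 rescued. With p̄ the pooled proportion, χ² = (a − b)² / [600·p̄(1 − p̄)].

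- Assigned scope, 24 vs 9 failures (success 92.0% vs 97.0%): 225/31.19 = 7.22, p = 0.007.
- Any scope, 14 vs 6 failures (95.3% vs 98.0%): 64/19.33 = 3.31, p = 0.069.
- Crossover, 12 vs 4 (4.0% vs 1.3%): 64/15.57 = 4.11, p = 0.043. Fisher's exact test gives 0.073.

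The two readings can fall on opposite sides of 0.05, but these counts were chosen to show that. They say nothing about how likely it is.

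**5. How open the wording is.** The plan lists success as *overall* and counts crossover separately, which leans towards success by any scope. Procedure time and radiation dose are both called *total*, which points to the whole procedure, counted in the randomised arm. Cannulation and fluoroscopy time are less clear. The data-collection line is general and does not say when scores are given. The interim sentence directly follows the sample size for complications and concerns conditional power. Nothing says that success by arm was examined.

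**The case for a change.** The strongest case for a change is that it would be cheap: a few lines would remove a choice that can move a stated comparison. The Background links disposable-cap scopes to rigidity, imaging issues and functional failure, which could plausibly force a switch. Counting every rescue as a success could then hide a device difference. The crossover outcome alone does not close the gap, because it misses failures that were never crossed over. Intention-to-treat does not close it either, because both readings comply with it.

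Most of this stands. Success is undefined, the rule for rescued procedures is absent, and which scope is scored after a switch is not stated. What does not follow is that the plan leads to a wrong result. Success including rescue answers a patient-level question and assigned-scope success answers a device question. Both keep the randomised comparison, and neither is the only correct one.

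The claim that a device difference could be hidden is also weakened. Besides crossover, the plan separately reports intubation at three checkpoints, suboptimal papillary positioning and use of advanced cannulation. The worry about interim looks rests on access to success results by arm, which the documents do not show. No analysis that drops crossed-over patients is planned, so there is no exclusion to guard against.

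**Conclusion.** The gap exists, but it is missing detail on secondary outcomes and calls for no change. An analyst would count patients in the arm to which they were randomised, state which version of success is reported and show crossover beside it, which the outcome list already provides. Either version is a valid comparison.

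The size cannot be determined from the documents. On assumed rates, with 40% of failures rescued by crossover, the choice of reading costs 24 points of power at 3% vs 8% (79% to 55%) and about 8 points at 3% vs 5% (24% to 16%). These figures assume equal crossover and rescue shares in both arms, and that every crossover follows a failure, although the plan also allows crossover for procedural difficulty. The primary complication outcome and the 600 patients do not depend on any of this.

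The study flow diagram is not shown and the data form is not part of the document, so neither could be checked for a definition.

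### Efficacy was assessed at several interim looks by conditional power, but the plan gives no efficacy boundary, alpha spending or adjusted final level, so the 5% error rate is not secured

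*Combined protocol and SAP*

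**What the plan says.** The sample-size paragraph under Outcome Measures sets the design: "The initial sample size was determined based on an expected complication rate of 7% in the CRD group and 14% in the DDEC group". It continues: "Assuming a 1:1 randomization, alpha error of 0.05, and study power of 80%, a total of 600 patients (300 per group) were required". Sidedness is not stated.

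The next sentence describes the looks: "Interim analyses were conducted during the study to assess efficacy and futility using conditional power analysis calculated with the frequentist Z-statistic method". The wording is plural and in the past tense, and efficacy is named as a purpose alongside futility.

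Under Data Collection and Analysis, the plan names chi-square or Fisher's exact tests for categorical variables and an intention-to-treat approach. Conditional power appears there only in the software list, where R is assigned to it.

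Nowhere does the document give the number or timing of the looks, the effect assumed for the remaining data, a conditional power threshold, an efficacy boundary, a spending function or a final significance level other than "alpha error of 0.05". No redaction mark or gap in these sections suggests that such a rule was removed.

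**The concern.** Conditional power (CP) is the probability, given the data so far, that the final test will be significant. It is a calculation and does not by itself control the error rate. Whether a CP rule holds 5% depends on the effect assumed for the remaining patients, the threshold, and the number and timing of the looks, none of which is stated.

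If a look could lead to a claim that one duodenoscope has more complications, the false-claim rate for the primary outcome depends on an unwritten rule. A reader could not interpret a final p-value just under 0.05. Because the 600 is described as the initial size, a reader also cannot tell whether a look changed enrolment.

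**Working it through.** **1. Reproduce the plan's sample size.** Inputs from Outcome Measures: 7% (CRD), 14% (DDEC), alpha 0.05, power 80%, 1:1 allocation. The mean rate is 0.105.

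n per arm = [z(alpha) × √(2 × 0.105 × 0.895) + z(power) × √(0.07 × 0.93 + 0.14 × 0.86)]² / 0.07²

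- Two-sided: (1.960 × 0.4335 + 0.8416 × 0.4307)² / 0.0049 = (0.8497 + 0.3625)² / 0.0049 = 299.88, so 300 per arm and 600 in total.
- One-sided: z(alpha) = 1.645 gives 236.1, so 237 per arm.

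The stated 600 is therefore the fixed, single-look, two-sided size. It contains no allowance for efficacy looks. Two-sidedness is inferred from this match.

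**2. Turn CP thresholds into interim cut-offs.** Let t be the information fraction and q the normal quantile of the threshold. With a final critical value of 1.96:

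- CP under the null: Z = (1.96 + q√(1 − t)) / √t
- CP under the observed trend: Z = √t × (1.96 + q√(1 − t))
- CP under the design effect: Z = (1.96 + q√(1 − t) − 2.80(1 − t)) / √t, where 2.80 = 1.96 + 0.84

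Example at t = 0.5 and a threshold of 80% (q = 0.8416): 1.96 + 0.8416 × 0.7071 = 2.555. The null cut-off is 2.555 / 0.7071 = 3.613. The trend cut-off is 2.555 × 0.7071 = 1.807, which is a nominal p of 0.071. The same threshold is very strict under one assumption and weaker than an ordinary 5% test under the other.

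**3. Overall two-sided type I error.** Assumptions: crossing the cut-off at a look leads to a claim, and otherwise the final test uses |Z| > 1.96. Results come from numerical integration or simulation of the sequential Z-statistic, for thresholds of 95, 90 and 80%.

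| Rule at the looks | One half-way look | Looks at 1/3 and 2/3 |
|---|---|---|
| CP under the null | 5.0, 5.0, 5.0% | 5.0, 5.0, 5.0% |
| Observed trend, early claims only for DDEC worse | 5.8, 6.4, 7.5% | 7.4, 8.6, 10.9% |
| Observed trend, early claims in both directions | 6.6, 7.7, 10.0% | 9.7, 12.2, 16.7% |
| As above, also needing nominal p < 0.05 | 6.6, 7.7, 8.3% | 9.2, 9.6, 10.5% |
| Design effect, early claims only for DDEC worse | 5.4, 6.2, 8.9% | 5.6, 7.3, 13.4% |

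The second row can be checked from the third. Allowing early claims on one side only gives about half the two-directional rate plus 2.5% for the other side. For example, 10.0 / 2 + 2.5 = 7.5%, and 16.7 / 2 + 2.5 = 10.85%. The last digit of the 10.9% depends on the method; integration gives 10.84%.

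Futility-only looks give 5.0% if non-binding and less than 5% if binding.

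**4. A boundary that does hold 5%.** Lan-DeMets O'Brien-Fleming-type spending, 0.025 per side, uses up 2[1 − Φ(2.241/√t)] per side by time t. At t = 0.5 this is 2[1 − Φ(3.170)] = 0.0015 per side.

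| Looks | Z boundaries | Two-sided nominal p | Power at 600 |
|---|---|---|---|
| Half-way, final | 2.963, 1.969 | 0.0031, 0.0490 | 79.9% |
| 1/3, 2/3, final | 3.710, 2.511, 1.993 | 0.0002, 0.0120, 0.0463 | 79.5% |

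**The case against.** The strongest reply is that the text shows a missing rule and not a faulty one. It says efficacy was assessed. It does not say that a look could stop the trial or support a claim, nor that 1.96 was used at the end. CP under the null would hold 5%, and futility-only looks would cause no inflation. All of this stands, and it limits the conclusion to an error rate that is not secured.

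A reader might infer from the table that the trial ran at 10% or 17%. The documents do not support that. Those cells need an 80% threshold under the observed trend with early claims in both directions, and hence a claim at nominal p = 0.071 half-way. Restricting early claims to the direction in which the plan expects the difference lowers them to 7.5% and 10.9%. Requiring nominal p < 0.05 as well, with both directions allowed, lowers them to 8.3% and 10.5%. Nor are any of these figures upper bounds, because the timing and thresholds are illustrative.

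The reply does not remove the point. Efficacy is a stated purpose of the looks, CP is the only interim method named, and the plan does not say which version was used. Its wording fits a 5.0% rule and rules well above 5% equally well.

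**Conclusion.** The concern holds as a gap in error control. The plan assesses efficacy at more than one look under a single alpha and a fixed-design sample size, with nothing that ties the looks to a 5% overall rate. Inflation is possible and has not been demonstrated.

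The size depends on the unstated rule: none for futility-only looks or CP under the null, and roughly 1 to 6 percentage points for CP under the observed trend with early claims only for DDEC worse (5.8 to 10.9% against 5%). It is more if early claims run both ways.

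Three assumptions carry these figures: the test is two-sided (inferred from the sample size), the final test is at 0.05 (no other level is given), and a look could lead to a claim. That the rule is missing is certain from the text; its effect on this trial's error rate is not known.

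**What to change.** Because the looks have already been made, disclosure comes first. State:

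- the number of looks and their information fractions;
- the effect assumed in CP and the threshold;
- whether a look could stop the trial or support an efficacy claim;
- whether any look changed the 600.

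What follows depends on the answers:

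- **Futility-only, or CP under the null at thresholds such as those above.** Say so, if that was in fact the rule. No new boundary is needed.
- **Any other rule under which a look could support a claim.** Base primary-outcome claims on a group-sequential boundary and not on CP, for example the spending function in step 4 at the actual information fractions. Choose it without reference to the results. If results by arm were already known, say that it was chosen afterwards. Report Z at every look.
- **An unblinded look changed the sample size.** Standard boundaries at the realised fractions do not in general protect the error rate. Use a combination or weighted test that does.

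In every case restate alpha, sidedness and power for the design actually used.

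**Cost.** If stopping follows the boundary, the loss at 600 patients is 0.1 points of power with one half-way look and 0.5 with two looks. Restoring 80% takes 602 or 608 patients. If the trial ran to 600, the practical change is a final level of 0.0490 or 0.0463.

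The cost is large only if the trial was stopped early on an observed-trend CP rule. Claiming only on the Lan-DeMets boundary after such a half-way stop (thresholds 80, 90, 95%) holds type I error at 3.2, 3.7 and 4.1% but leaves power of about 42, 50 and 56%. No passage says that this happened. If it did, the loss cannot be recovered and should be disclosed.
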